6.1 Primary Endpoint

Change in Alpha Frequency Electrical Activity in Left Frontal Cortex from Stimulation [Time Frame: 8-minute recording before vs after intervention]

6.2 Secondary Endpoint

Difference in magnitude of effect of tACS on left prefrontal alpha in follicular vs luteal phase.

6.3 Statistical Methods

Baseline Data: alpha oscillations in left frontal cortex before stimulation; severity of luteal phase symptoms in screening DRSP.

Efficacy Analysis: This is repeated, single intervention (tACS) administered during the follicular and luteal phase. Change in left prefrontal alpha power on EEG is the primary outcome. Effect of menstrual cycle phase is the secondary outcome. We will use a t-test of pre-post changes to examine effects of tACS on left prefrontal alpha oscillations (primary outcome) and differences in effects as function of menstrual cycle phase (secondary outcome). There will be two levels of each of the two repeated within-subjects measures (pre vs post stimulation and follicular vs luteal phase). Order of administration will be assessed by considering order as a between- subjects variable.

Exploratory analysis: Assessment of possible changes in mood will be assessed with linear mixed model regression analysis comparing mean luteal phase core affective symptoms (depression, irritability) after stimulation with means during baseline.

Pharmacokinetic Analysis (if applicable): not applicable

Safety Analysis - The PI will review any adverse effects and will quarterly review aggregated data, which will be recorded descriptively. Safety/ Tolerability will be assessed in two ways: 1) with somatic symptoms contained within the DRSP, completed daily, and with symptoms reviewed daily by the research coordinator. Any symptoms of moderate or greater severity appearing proximate to the tACS session will be reported to the PI. 2) with a semi-structured interview at the end of each tACS session, inquiring about possible side effects during the procedure (e.g., tingling, flickering lights, itching, burning sensation, headache, neck pain, scalp pain). Side effects of moderate or greater severity will be reported to the PI, who will also review aggregate data at the end of the experiment.

6.4 Sample Size and Power - The main intent of this study is to conduct a pilot study, the results of which could be used in a larger trial that is appropriately powered for efficacy. Nonetheless, we intend to determine whether tACS influences alpha coherence on EEG. Due to the novelty of the application, we do not have all the required parameters to estimate the power for the repeated measure design on alpha coherence on EEG. However, the primary purpose is to demonstrate tACS associated changes in alpha coherence and whether that differs by cycle phase. The aim to demonstrate ‘target engagement’ does not necessarily lend itself to traditional power calculations and we will rely on [name] extensive experience with analyzing these data. In his experience, he is confident that if, in fact, if there are menstrual cycle differences in alpha coherence, 20 participants will be sufficient to demonstrate that effect.

Due to the novelty of the application, we do not have all the required parameters to estimate the power for the repeated measure design on alpha coherence on EEG. Nonetheless, preliminary data from a study of five tACS sessions in a study of patients with major depression showed a significant alteration in left frontal alpha power following 10Hz stimulation in a sample of 10 subjects ($p < .05$, paired t-test with FDR correction). Notably, there was no significant difference between results after one and five sessions. As such, we are confident that a sample size of 20 should enable us to establish target engagement as well as determine whether there are meaningful menstrual cycle differences in alpha coherence.

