To ensure appropriate blinding for each stimulation session, there are designated unblinded individuals to ensure the appropriate stimulation parameters are applied to each participant. These individuals will not interact with participants and will only be involved with the creation of a study file and validation of stimulation waveform.

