When comparing input of energy into the subject, both the amount of current and the area over which this current is dispersed are critically important. The value of interest is called the current density, which is the amount of current divided by the area. Our stimulation area is 25 cm². Therefore, we will use this device at 2mA, resulting in a current density of 0.08mA/cm². Our use of this transcranial current stimulation device poses 'minimal risk' to subjects because of the low current density being applied. Our application of current will result in an equivalent current density as performed in prior studies, in which subjects experienced no serious side-effects or harm. Prior studies using other brain stimulators have used a range of current densities: (Iyer, Mattu et al. 2005) used a maximum current density 0.08mA/cm², conducted at NINDS with DC stimulators, and (Groppa, Bergmann et al. 2010) used a maximum current density of 0.125mA/cm² with no reported side effects

With use of this technology, some subjects report transient tingling underneath the electrode on the scalp, itching, headache, burning sensation, and discomfort. However, a recent meta-review has

failed to find any significant difference in occurrence rates between transcranial current stimulation and sham control itching (39.3% vs. 32.9%, $p>0.05$), tingling (22.2% vs. 18.3%, $p>0.05$), headache (14.8% vs. 16.2%, $p>0.05$), burning sensation (8.7% vs. 10%, $p>0.05$) and discomfort (10.4% vs. 13.4%, $p>0.05$). (Brunoni, Amadera et al. 2011). In our experience, increased sleepiness and flickering lights were more common than sham stimulation. During stimulation, the research assistant will ask the subject about her comfort level. If the subject reports any pain, stimulation will immediately be stopped.

EEG: EEG is a commonly used measure and is not associated with adverse events. Individuals may find the electrode gel annoying, as hair will require shampooing after the conclusion of the EEG.

Embarrassment: Self-report assessments contain questions regarding sensitive personal information. This risk is necessary to assess mood symptoms and psychopathology. Subjects will be assured upon intake that only study personnel will see associated DRSP responses.

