3 INVESTIGATIONAL PLAN

3.1 Study Design

Repeated measure, open-label study design.

Overview of study phases:

- **Screening/Baseline:** subjects will be followed for three months in a related protocol to document that subjects meet criteria for PMDD, showing affective symptoms of requisite severity as present during the luteal phase and relatively absent during the follicular phase.
- **Intervention/Treatment:** a single 40-minute session of tACS, administered once each in the follicular and luteal phases of the menstrual cycle

- **Follow up:** subjects will be followed with daily ratings until completion of the menstrual cycle following the second tACS. Any subject endorsing suicidal ideation, severe deterioration of mood, or distressing somatic symptoms on daily rating forms will be referred to [name] for acute evaluation and determination of appropriate subsequent clinical response.
- **Unscheduled Visits:** not applicable

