3.2 Allocation to Treatment Groups and Blinding (if applicable): Not applicable

3.3 Study Duration, Enrollment and Number of Subjects

The study is anticipated to last five years. After being shown as eligible (in our screening protocol), subjects will sign an informed consent form and be deemed as enrolled when they have participated in the first tACS session. We will enroll 22 subjects to accommodate a 10% drop-out and achieve a sample size of 20. Each subject's participation is expected to last approximately one month. Two tACS sessions with pre-post EEG recordings will occur, one during the follicular phase (5-9 days after menstruation) and one in the luteal, premenstrual phase (9-13 days after ovulation). Subjects will test their urine at home each morning for approximately one week to determine ovulation. Each tACS/EEG session will last up to 90 minutes. There will be approximately 20 people in this research study.

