10 DATA COLLECTION AND MANAGEMENT

Daily Record of Severity of Problems (DRSP) responses will be collected using study ID number as the identifier, stored by Qualtrics survey software and will be monitored to ensure consistency and completion of responses. Symptom ratings will be used for safety during the study..

EEG recordings will be kept on a secure server within the Department of Psychiatry and will be analyzed by [name].

Participants will be identified by study ID number on all research documents and in electronic data files. All data will be stored in locked cabinets inside locked offices, and electronic data will be stored only on password-protected file servers only accessible from computers in the Psychiatry Department. Only study personnel will have access to these data. Qualtrics will be used to collect self-report questionnaire data for all participants. Participants will not enter any personally identifying information into the Qualtrics system, and they will be identified by their unique study ID only.

The document that associates subject names and study ID numbers will be destroyed 5 years following the last publication to come from the study. Consent forms and any other documentation containing subject information other than study ID will be destroyed at this time as well. Paper documentation will be shredded, and computerized data will be permanently deleted from the lab server. Subject names and contact information will be maintained indefinitely for the purpose of future studies and stored in a secure, password-protected database that meets UNC standards for data security as determined by department IT security specialists.

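### The primary pre-post change in left frontal alpha has no control condition and no described masking of EEG processing, so by itself it cannot be claimed as an effect of tACS or as target engagement

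*Combined protocol and SAP*

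**What the plan says.** Section 3.1 describes the design: "Repeated measure, open-label study design". Under sections 4.1 and 4.2 each woman receives active tACS once in each cycle phase, in counterbalanced order. Section 8 randomises only which phase comes first. Section 5 places the resting EEGs immediately before and after the 40 minutes of stimulation.

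The primary analysis in section 6.3, repeated in the synopsis, reads: "We will use a t-test of pre-post changes to examine effects of tACS on left prefrontal alpha oscillations (primary outcome". The opening of section 6 gives a repeated-measures ANOVA with a pre/post time factor instead. Section 6.1 defines the endpoint as a change, without direction or threshold, while objective 2.1.1 is a decrease.

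On blinding, the plan has "3.2 Allocation to Treatment Groups and Blinding (if applicable): Not applicable", and section 8 says the same. Sections 1 and 7 nevertheless say "To ensure appropriate blinding for each stimulation session, there are designated unblinded individuals". On EEG handling, section 10 says only "EEG recordings will be kept on a secure server within the Department of Psychiatry and will be analyzed by" a named team member.

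On what the result is for, the section 1 introduction calls target engagement a necessary first step. The protocol history in section 1 makes a follow-up efficacy study depend on it. Section 6.4 expresses confidence that 20 women suffice to establish it.

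**The concern.** The plan moves from a before-after difference to a stimulation effect with nothing in the design to support that step. No sham session, no-stimulation session or control group is described, and no vigilance measure. Randomising phase order balances follicular against luteal. It does nothing about the 40 minutes that separate every pre recording from its post recording. The ANOVA has the same gap, because its time factor is also uncontrolled.

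A second route to bias is processing. Artefact rejection and alpha extraction usually involve judgement, and no step is described that hides pre/post or phase from the person doing them.

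A significant result is meant to trigger an efficacy study. If time, repeat recording or processing produced the change, that study would start on a false premise.

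**Working it through.** **Inputs from the documents.** 20 completers and 22 enrolled (section 3.3); paired pre-post t-test (section 6.3). The enrolment figure reproduces as 20 × 1.10 = 22 (20/0.9 = 22.2 by the other convention). The 20 itself cannot be reproduced: section 6.4 says the parameters for a power calculation are lacking.

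**Assumed.** Two-sided 0.05 (neither level nor sidedness is stated), normally distributed change scores, zero stimulation effect, and a non-stimulation drift of *d* SD of the change score tested.

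**Threshold.** The critical value is t(0.975; 19 df) = 2.093. The smallest significant mean change is 2.093/√20 = 0.468 SD, whatever caused it.

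**Rejection probability.** With λ = d√20, P(reject) = P(T > 2.093) + P(T < −2.093), where T is noncentral t with 19 df and noncentrality λ.

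| Drift d (SD) | λ | Declared significant |
|---|---|---|
| 0 | 0 | 5% |
| 0.2 | 0.894 | 14% |
| 0.3 | 1.342 | 25% |
| 0.4 | 1.789 | 40% |
| 0.5 | 2.236 | 56% |
| 0.8 | 3.578 | 92% |

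A one-sided 0.05 test in the direction of the drift gives 22% at 0.2 SD and 70% at 0.5 SD (69.5% before rounding). If the two sessions are averaged, as in the ANOVA time effect, a per-session drift d becomes d/√((1+ρ)/2). A drift of 0.5 SD is then declared in 69% (ρ = 0.5) to 85% (ρ = 0) of trials.

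**Check with a control.** In 40,000 simulated trials per drift value, with the same drift in a sham condition and no stimulation effect, the sham contrast rejected in 4.8% to 5.1%. The excess therefore comes from the missing control, not from the t-test.

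**In percentage terms.** A drift to a fraction k of baseline is d = |ln k|/SD, with the SD of the log change also assumed.

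| Drift in alpha | SD 0.25 | SD 0.35 | SD 0.50 |
|---|---|---|---|
| 5% | 14% | 10% | 7% |
| 10% | 43% | 25% | 15% |
| 20% | 97% | 77% | 47% |

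**Preliminary data.** Read as a plain paired t-test, p < .05 at n = 10 (section 6.4) implies an observed change of at least 2.262/√10 = 0.715 SD. A true mean change of that size would be significant at n = 20 in 86% of trials, whether stimulation or drift produced it. The text reports no sham comparison for that result.

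**The case against.** The open-label pilot design is disclosed, and the protocol history explains that a sham-controlled design failed to recruit, largely because of its many daily sessions. Alternating eyes-open and eyes-closed blocks standardise the recordings. A proportional drift common to both hemispheres would largely cancel from the asymmetry in objective 2.1.2, and a drift equal in both phases cancels from the follicular-luteal comparison. An upward drift would count against an objective stated as a decrease. These points stand, but they leave the section 6.1 endpoint uncontrolled: it is left frontal only, and standardised blocks do not remove time effects.

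A reader might infer more than the documents support:

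- **That the EEG analysis is unblinded.** No section says so. Not applicable in 3.2 and 8 concerns allocation and administration, and section 10 is silent. What can be said is that masking is not described.
- **That drowsiness lets engagement be declared with no stimulation effect.** Section 1.1 reports that "increased sleepiness and flickering lights were more common than sham stimulation", but the synopsis's data and safety monitoring plan names only flickering lights as differing between groups. Sleepiness in excess of sham would itself be caused by stimulation: a non-specific effect, not an absent one. How vigilance affects alpha is not in the documents.
- **That the false-positive rate is known to be high.** Drift, its direction and the SD are all assumed. At 5% drift the rate is 14% or less for the SDs shown.
- **That a specificity contrast must be passed before success is claimed.** This is a trade-off. With a true frontal effect of 0.715 SD, no posterior effect, equal SDs and uncorrelated changes (all assumed), the contrast is 0.715/√2 = 0.506 SD and power at n = 20 falls from 86% to 57%. It also need not cancel drowsiness, which may differ by site and band.

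**Conclusion.** The concern holds in a limited form. The primary test cannot distinguish a tACS effect from elapsed time or repeat recording, and processing bias is not excluded because masking is not described. With no stimulation effect, a drift of 0.2 to 0.5 SD would be declared significant in 14% to 56% of trials (n = 20, two-sided 0.05). That range illustrates sensitivity to an assumed drift and does not estimate this trial's error rate. The weakness lies mainly in the conclusion drawn: a before-after change is supportable, but target engagement established by this test alone is not. The secondary phase comparison is less affected.

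**What to change.** 1. **Section 10:** state that existing study staff not involved in the EEG analysis will recode the four EEG files per woman. Artefact rejection and alpha extraction are to be completed and locked before pre/post, phase and order codes are released.
2. **Section 6.3 and the synopsis:** state that the primary result will be reported as a change from before to after the tACS session. State that, without a control condition, it will not alone be claimed as an effect of tACS or as established target engagement. Align the section 1 introduction, the protocol history and section 6.4.
3. **Optional:** if the montage allows, prespecify frontal-minus-posterior and alpha-minus-other-band changes as supportive analyses, with electrodes and bands named. The right frontal site is not an unstimulated control, because F3 and F4 are both stimulated.
4. **Consistency:** reconcile the blinding text in sections 1 and 7, which concerns stimulation set-up, with not applicable in 3.2 and 8. Reconcile the two statements on sleepiness.

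The cost is minor file handling and a more modest conclusion. Items 1, 2 and 4 need no extra participants, sessions or sham arm.
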